## CLINICAL TRIAL PROTOCOL SYNOPSIS

Name of company:		Boehringer Ingelheim	
Name of finished product:		Spiolto ® Respimat ® inhalation solution	
Name of active ingredient:		Tiotropium + olodaterol fixed dose combination inhalation solution - Respimat ®	
Protocol date: 25 Oct 2016	Trial number: 1237.36		Revision date: 30 Nov 2017
Title of trial:	An exploratory, randomised, double-blind, double-dummy, active-controlled, two period cross-over study to investigate the effect of 6 weeks treatment of orally inhaled tiotropium + olodaterol fixed dose combination (FDC) delivered by the Respimat ® Inhaler with fluticasone propionate + salmeterol FDC delivered by the Accuhaler ® Inhaler, on left ventricular function and arterial stiffness in patients with Chronic Obstructive Pulmonary Disease (COPD)		
Coordinating Investigator	Phone: _____, Fax: _____		
Trial site(s):	Multi-centre trial (approximately 10 centres in Germany)		
Clinical phase:	IV		
Objective(s):	The primary objective of the study is to explore the effect of treatment with tiotropium + olodaterol FDC compared to fluticasone propionate + salmeterol FDC on reversal of left ventricular diastolic dysfunction assessed with cardiac magnetic resonance (CMR) imaging. A secondary objective is to explore the effect of tiotropium + olodaterol FDC compared to fluticasone propionate + salmeterol FDC on measures of arterial stiffness assessed by CMR and central blood pressure assessed by pulse wave analysis (PWA), and on reduction of lung hyperinflation assessed with body plethysmography (pleth) and post dose spirometry.		
Methodology:	Exploratory, randomised, double-blind, double-dummy, active-controlled, cross-over design comparing two treatments after 6 weeks of treatment.		

Name of company:		Boehringer Ingelheim	
Name of finished product:		Spiolto ® Respimat ® inhalation solution	
Name of active ingredient:		Tiotropium + olodaterol fixed dose combination inhalation solution - Respimat ®	
Protocol date: 25 Oct 2016	Trial number: 1237.36		Revision date: 30 Nov 2017
No. of patients:	Approximately 74		
total entered:	Approximately 74		
each treatment:	Approximately 74		
Diagnosis :	Chronic Obstructive Pulmonary Disease (COPD)		
Main criteria for inclusion:	Outpatients of either sex, aged $\geq 40$ years and $\leq 75$ years with smoking history $> 10$ pack years, post bronchodilator FEV 1 $< 70\%$ predicted, post-bronchodilator FEV 1 /FVC $< 70\%$ , FRC pleth $> 120\%$ predicted normal, with post-bronchodilator reversibility which improves by greater than or equal to 7,5 percentage points, clinically free of cardiovascular (CV) disease.		
Test product(s):	Tiotropium + olodaterol FDC inhalation solution - Respimat ®		
dose:	[5 µg tiotropium + 5 µg olodaterol] (2.5 µg / 2.5 µg per actuation)		
mode of administration:	Oral inhalation (2 inhalations in the morning)		
Comparator products:	Fluticasone propionate + salmeterol FDC dry powder for inhalation - Accuhaler ®		
dose:	[1000 µg fluticasone propionate + 100 µg salmeterol] (500 µg / 50 µg per actuation)		
mode of administration:	Oral inhalation (2 x 1 inhalation daily) bid		

Name of company:		Boehringer Ingelheim	
Name of finished product:		Spiolto ® Respimat ® inhalation solution	
Name of active ingredient:		Tiotropium + olodaterol fixed dose combination inhalation solution - Respimat ®	
Protocol date: 25 Oct 2016	Trial number: 1237.36		Revision date: 30 Nov 2017
Duration of treatment:	2 x 6-week treatment periods (total treatment duration of 12 weeks)		
Endpoints	
Primary endpoint is change from baseline in left ventricular end diastolic volume index (LVEDVI) after 6 weeks of treatment.
 
Secondary endpoints, all calculated as change from baseline, include:          Aortic distensibility, pulmonary artery pulsatility.          Central systolic, pulse and augmentation index.          FRCpleth % predicted after 6 weeks of treatment.          1,5 hour post dose FEV1, after 6 weeks of treatment.          1,5 hour post dose FVC, after 6 weeks of treatment.
		
Safety criteria:	Heart rate and blood pressure in conjunction with lung function testing as applicable, adverse events and physical examination.		
Statistical methods:	
Restricted Maximum Likelihood (REML) estimation based Mixed-effects Model for Repeated Measures (MMRM) analysis will be used to obtain adjusted means for the treatment effects.          This model will include treatment and period as fixed effects, patient as a random effect and baseline as a covariate. (Unstructured covariance structure will be used for within patient variation).
 
Descriptive statistics for the safety analyses/assessment.
		

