## 5. VARIABLES AND THEIR ASSESSMENT

### 5.1 TRIAL ENDPOINTS

#### 5.1.1 Primary Endpoint(s)

The primary endpoint is change from baseline in LVEDVI in the 6th week of treatment with tiotropium+olodaterol FDC versus fluticasone propionate+salmeterol FDC.

LVEDVI is normalized left ventricular end diastolic volume (LVEDV), divided by body surface area (BSA) ([Appendix 10.3](#)).

Baseline is defined as the value obtained during the assessment performed in a week prior to Visit 2. The change from baseline is calculated as the value obtained in a week prior to Visits 3 and 4 (end of each treatment periods) minus the baseline value.

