#### 5.1.2 Secondary Endpoint(s)

The following secondary endpoints will be evaluated, all calculated as a change from baseline after 6 weeks of treatment:

- Aortic distensibility and pulmonary artery (PA) pulsatility.
- Central systolic pressure, pulse pressure and augmentation index (AI).
- FRCpleth % predicted.
- 1,5 hour post dose FEV1.
- 1,5 hour post dose FVC.

None of the primary or secondary endpoints are safety issues.

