### 7.3 PLANNED ANALYSES

The efficacy analysis will be performed in all randomised patients who were documented to have received any dose of trial medication and who have both baseline and any evaluable post-baseline measurement for the primary endpoint or secondary endpoints. This set will be called Full Analysis Set (FAS).

The data from patients who have had an exacerbation during the treatments will be excluded from the analyses,

All randomised patients taking any dose of the trial medication will be included in the safety evaluation (Treated Set).

The handling of randomised patients who received the wrong treatment will be specified in the Trial Statistical Analysis Plan (TSAP).

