### 7.3.1 Primary endpoint analyses

In the primary analysis, the two-sided hypothesis as given in [Section 7.2](#) will be tested based on adjusted mean change from baseline in LVEDVI, as listed in [Section 5.1.1](#), using a restricted maximum likelihood (REML)-based MMRM. This model will include treatment and period as fixed effects, patient as a random effect and baseline as covariate. Unstructured covariance structure will be used for within patient variation. If convergence is not achieved, the compound symmetry covariance structure will be used. The SAS procedure MIXED will be used involving the restricted maximum likelihood estimation and the Kenward-Roger approximation for denominator degrees of freedom. This approach is described in [[R10-4391](#)]. Adjusted mean values as well as treatment contrasts will be presented together with the 95% confidence intervals (CI) and p-values.

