6.3 PATIENT SETS ANALYSED

The following nested patient sets are defined:

- Randomised set (RS):

This patient set includes all patients who signed informed consent form and were also randomised, regardless whether the patient was treated with study medication or not.

- Treated set (TS):

This patient set is nested within RS and includes all patients who were dispensed study medication and were documented to have taken any dose of study medication. TS will be used for patient disposition, demographics and baseline disease characteristics, concomitant therapies, treatment compliance, treatment exposure and safety analyses (including AEs and vital signs).

- Full analysis set (FAS):

This patient set is nested within TS and includes patients who had baseline measurement and at least one post-baseline measurement for the primary endpoint or secondary endpoints. Assignment to the FAS will be done after implementation of any data handling rules which set measurements to missing.

- Full analysis set excluding exacerbation (FAS-EE):

This patient set is nested within FAS and the data from patients who have had an exacerbation during the treatments will be excluded from this data set. FAS-EE will be used for the efficacy analyses.

- Per protocol set (PPS):

This patient set is nested within FAS-EE and includes only patients who had no important PVs which are specified to be excluded from the PPS (Table 6.3: 1).

The final decision regarding which patients are excluded from PPS will be made at BRPM or data base lock meeting (DBLM) prior to data unblinding.

Table 6.3: 1 Patient sets analysed

		Patient Sets
Class of endpoint	TS	FAS-EE
Primary endpoint		primary analysis
Secondary endpoints		X
Safety endpoints	X	
Demographic/baseline endpoints/exposure	X	

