6.6 HANDLING OF MISSING DATA AND OUTLIERS

As noted in the protocol, in general, missing data at a given visit will be imputed by the available data from the patient at that visit and completely missing visits will be handled through the statistical model.

Completely missing visits will not be imputed and will stay as missing, and will be handled in the mixed model repeated measures model.

It could happen that a patient needed therapy for COPD symptoms at a clinic visit. This therapy was entered on the rescue medication electronic Case Report Form (eCRF). This may or may not be the rescue medication provided by Boehringer Ingelheim (BI). For purposes of the imputation rules this will be termed “rescue medication” regardless of whether or not it was BI-supplied rescue medication.

The following rules will be used for spirometry data which were collected at Visits 2, 3 and 4:

- Since there is only one spirometry measurement at each on-treatment clinic visit, rescue medication use on or before the spirometry measurement or rescue use with unknown time will both result in all spirometry measurements for the visit being set to missing.

- Randomly missing spirometry measurements at Visits 2, 3, and 4, e.g., due to a mechanical failure, will not be imputed.

The rules used for spirometry data will also be applied to Body Plethysmography. CMR data will not be imputed.

Missing or incomplete AE dates are imputed according to BI standards (see “Handling of missing and incomplete AE dates”) (3).

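### For FEV1, FVC and FRC, the planned model drops patients with valid Visit 3 and Visit 4 values when the Visit 2 baseline is missing, although that baseline adds almost nothing to the treatment contrast

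*Protocol*

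**What the plan says.** The protocol synopsis describes a REML-based repeated-measures model with treatment and period as fixed effects, "patient as a random effect and baseline as a covariate". Protocol 7.3.1 and SAP 7.4 specify unstructured covariance and add a fallback: "If convergence is not achieved, the compound symmetry covariance structure will be used". Protocol 7.3.2 and SAP 7.5.2 carry this model over to the secondary endpoints, which protocol 5.1.2 defines as "all calculated as a change from baseline after 6 weeks of treatment".

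Each patient has one baseline for both periods. For LVEDVI, protocol 5.1.1 states: "Baseline is defined as the value obtained during the assessment performed in a week prior to Visit 2". For endpoints not derived from CMR, SAP 6.7 uses the pre-dose value at Visit 2.

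Protocol 7.3 limits the Full Analysis Set to treated patients "who have both baseline and any evaluable post-baseline measurement for the primary endpoint or secondary endpoints". SAP 6.3 fixes the order of operations: "Assignment to the FAS will be done after implementation of any data handling rules which set measurements to missing".

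SAP 6.6 introduces its spirometry rules as covering Visits 2, 3 and 4. Rescue use before or at the measurement, or at an unknown time, sets the visit's spirometry to missing. It also says: "Randomly missing spirometry measurements at Visits 2, 3, and 4, e.g., due to a mechanical failure, will not be imputed". The same rules apply to plethysmography. Completely missing visits are left to the statistical model.

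**The concern.** A likelihood-based model can accommodate a missing response at Visit 3 or Visit 4. It cannot do the same for Visit 2, because Visit 2 is used as a covariate and is also subtracted from both responses. One missing baseline therefore removes both on-treatment values. The FAS does not help: a patient may enter it on another endpoint, but the lung-function model still omits that patient.

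Protocol 3.2 justifies the crossover on the ground that treatments are compared within the patient. The two on-treatment values carry that comparison, so discarding a complete pair for want of a pre-treatment value gives up information that the design was chosen to obtain. At stake is the precision of the FEV1, FVC and FRC contrasts, which serve the secondary objective on hyperinflation and post-dose spirometry.

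**Working it through.** **1. The plan's own figure.** Protocol 7.7 gives 74 patients for 80% power with a difference of 2.5 mL/m², SD 7.5 and two-sided alpha 0.05. Taking 7.5 as the SD of the within-patient difference, with a noncentral t on N − 2 degrees of freedom and even N, all six rows of Table 7.7:1 reproduce (52, 68, 74, 98, 74, 98). Power at N = 74 is 80.8%. The calculation contains no allowance for lost patients.

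**2. Why the baseline hardly enters the contrast.** Let Y1 and Y2 be the Visit 3 and Visit 4 values and B the baseline. Then (Y1 − B) − (Y2 − B) = Y1 − Y2, so the subtraction cancels. As a covariate, B is constant within a patient. Under compound symmetry with complete pairs the contrast uses only within-patient differences, so B has no influence. Under unstructured covariance, unequal estimated period variances let the patient total act as an adjuster, and B enters indirectly.

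**3. Numerical check.** Inputs: 74 patients allocated 1:1 to AB or BA, difference 2.5, SD of differences 7.5 and between-patient SD 12 (assumed), with 60 simulated data sets per setting. Standard errors are model-based REML values without the Kenward–Roger adjustment. The LVEDVI scale is used because the documents give no SD for lung function, so only the relative changes matter here. Reduction = 1 − (SE with baseline / SE without).

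| Covariance | Visit 4 missing | Mean SE, raw values, no baseline | Mean SE, change with baseline covariate | Reduction |
|---|---|---|---|---|
| Compound symmetry | none | 0.8693 | 0.8693 | 0.0% |
| Compound symmetry | 10% | 0.8991 | 0.8903 | 1.0% |
| Compound symmetry | 20% | 0.9604 | 0.9396 | 2.2% |
| Unstructured | none | 0.8677 | 0.8668 | 0.1% |
| Unstructured | 10% | 0.9006 | 0.8930 | 0.8% |
| Unstructured | 20% | 0.9450 | 0.9269 | 1.9% |

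With complete data the estimates were identical under compound symmetry. Under unstructured covariance a single estimate moved by up to 0.58 mL/m², with precision almost unchanged.

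**4. Cost of losing pairs.** The standard error is proportional to 1/√N, so the widening factor is √(74/N′), where N′ is the number of pairs kept. The missing rates are assumptions.

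| Pairs lost | N′ | √(74/N′) | Widening |
|---|---|---|---|
| 1 | 73 | 1.007 | 0.7% |
| 4 (5%) | 70 | 1.028 | 2.8% |
| 7 (9%) | 67 | 1.051 | 5.1% |
| 11 (15%) | 63 | 1.084 | 8.4% |
| 15 (20%) | 59 | 1.120 | 12.0% |

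**5. Baseline as a pre-treatment response.** With 7 of 74 baselines missing, mean SE under unstructured REML fell from 0.892 as planned to 0.846 (0.846/0.892 = 0.948, or 5.2% lower). With none missing it was 0.870 as planned and 0.864 with the change. Complete-data estimates moved by up to 0.24 mL/m² in one set of simulations. In another they moved by 0.06 on average and 0.34 at most.

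**The case against.** The strongest reply is that the documents largely prevent the gap. Protocol 4.2.1 has lung-function tests at Visits 2 to 4 repeated on another day if rescue is needed. Sections 4.2.2.2 and 6.1 allow rescheduling for washout failure. Section 6.2.2 lists the Visit 2 tests before the randomisation call. Exclusion criterion 27 removes patients who cannot comply with the medication restrictions. In addition, the reason SAP 6.6 gives for its rescue rule refers to visits on treatment, so its application to the baseline is not certain. All of this stands, and it limits the loss. It does not eliminate it: the rules are introduced as covering Visit 2, the non-imputation rule names Visit 2 explicitly, and no provision covers a baseline that stays missing.

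A second reply is that requiring a baseline follows from endpoints defined as change from baseline. That is true of the adjusted mean changes. The treatment contrast, however, is the same quantity on either scale.

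Four stronger readings are tempting, and the documents do not support them:

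- **All endpoints lose patients.** The model requirement is general, but baseline CMR is needed before randomisation to check ejection fraction, so LVEDVI is little affected. Neither CMR nor pulse wave analysis has a rescue-deletion rule, and the documents do not mention unreadable vessel planes.
- **The baseline cancels exactly and gives no gain.** This holds only for complete pairs under compound symmetry, which is the fallback structure.
- **Power falls below 80%.** The power calculation concerns LVEDVI. No SD, target difference or power is stated for lung function, and those p-values are descriptive.
- **The loss falls mainly on patients who cannot do without rescue.** Many of these would be retested or never randomised, so the documents do not establish that pattern.

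**Conclusion.** The point holds for FEV1, FVC and FRC as a modest, avoidable loss of precision. A missing Visit 2 value removes a complete on-treatment pair, while the baseline is worth about 0.1% in mean standard error for complete pairs and about 1–2% when 10–20% of patients contribute one period. The interval would be about 3% wider with 4 of 74 baselines missing and about 5% wider with 7 of 74.

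The true rate is not given and may be small. The simulated figures rest on an assumed between-patient SD of 12 and on LVEDVI-scale inputs. The widening factor needs only that the variance per pair stays the same.

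**What to change.** In SAP 6.3 and 7.5.2, for FEV1, FVC and FRC, estimate the treatment contrast from the Visit 3 and Visit 4 values, with baseline entered as an additional pre-treatment response. Membership of the analysis set for these endpoints should then require an on-treatment value but not a baseline, so every such patient contributes. At minimum, prespecify this as a sensitivity analysis.

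The SAP should say that the contrast is not systematically changed for complete data. It should not say that the result is identical, because individual estimates do move under unstructured covariance. Keep the adjusted mean changes from baseline as a display in patients who have a baseline. State in SAP 6.6 whether the rescue rule applies to the Visit 2 baseline.

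The cost is SAP wording, minor programming, and slightly different patient numbers in the contrast and the change-from-baseline table, which a footnote can explain.

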## FLOW CHART

	Screening period Run-in Period		Treatment phase			Discontinuation 	Follow-up
	0	1	2	3 	4 		
			Period 1 and 2				
Visit	0	1	2	3 	4 		5
Week of treatment (cumulative)	-	-3 to -1	0	6	12 EoT		V4 + 3 EoO
Day of treatment	-	-21 to -7	1	43	85		106
Day of treatment (cumulative) Time window (days)*	-	-21 to -7	1	43 ±3	85 ±3		V4 + 21 +7
Informed consent, patient information	X 						
Register patient in screening (IRT)	X						
Demographics		X					
Medical history/Baseline Conditions		X					
COPD/patient characteristics		X					
Smoking status		X	X	X	X	X	
In-/Exclusion criteria		X	X				
Physical examination		X		X	X	X	X 
Laboratory tests		X					
Pregnancy test 		X	X	X	X	X	X
12 lead-ECG 		X					
Training in use of Respimat ® and Accuhaler ®		X	X 	X 			
Randomisation (IRT)			X				
Medication washout check		X	X	X	X		
Dispense and explain use of rescue medication	X 	X	X	X			
Collect rescue medication		X	X	X	X	X	
Dispense trial medication (IRT)			X	X			
Administer trial medication at clinic			X	X	X		
Collect trial medication				X 	X 	X	
Drug and/or rescue med. accountability check mMRC 		X	X	X	X		
Cardiac Magnetic Resonance (CMR) 			X 11a	X 11b	X 11b		
Body Plethysmography (FRC, RVol, TLC, IC)		X 	X 	X 	X 		
Spirometry (FEV 1 , FVC)		X 	X 	X 	X 	X	
Vital signs (seated) 		X	X	X	X	X	
Blood pressure and PWA 		X	X	X	X		
Adverse events		X	X	X	X	X	X
Concomitant therapy		X	X	X	X	X	X
Medication washout		X	X	X	X		
Rescue Medication Use 		X	X	X	X	X	
Trial Medication Adherence 				X	X	X	
Telephone contacts 		X	X	X	X		
Trial medication termination (IRT)					X	X	
Completion of patient participation							X

- \* Site should make every effort to attain 6 weeks treatment exactly when scheduling the visit days with the patient at the beginning of the trial.
- 1 Treatment phase: Procedures during visits 3 and 4 will be identical.
- 2 Informed Consent: All patients must sign an informed consent consistent with ICH-GCP guidelines prior to participation in the trial, which includes medical washout and restrictions.
- 3 Premature discontinuation procedures and observations: To be completed by all patients who took at least one dose of trial medication including those who discontinue early (see [Section 6.2.3](#)).
- 4 End of observation (EoO) examinations: To be performed in the event of any clinically relevant findings at Visit 4.
- 5 Pregnancy testing: Women of child-bearing potential: serum pregnancy test at Visit 1; urine pregnancy test at Visits 2, 3, 4 and 5.
- 6 ECG: 12-lead ECG recording at screening (Visit 1) for inclusion in the study.
- 7 Device training: The patient will be instructed in the use of the Respimat® inhaler and Accuhaler® inhaler, but the patient **should not** inhale from the placebo/demonstrational inhaler at these visits.
- 8 Rescue medication: To be supplied to all patients at Visit 0.
- 9 Trial Medication collection: Last dose of trial medication for the respective treatment period will be the morning dose, taken in the clinic on visit day (Visit 3 – day 43 and Visit 4 – day 85). All medication is collected after this dosing.
- 10 mMRC ; Refer to [Appendix 10.4](#) and [10.5](#), respectively.
- 11 Cardiovascular MR:  
11a - baseline evaluation - in a week prior to randomisation (Visit 2) but at the latest 3 days prior to the Visit 2 to allow for the assessment of ejection fraction level for inclusion.  
11b - end of treatment evaluation - in a week prior to end of treatment period visits or on the visit day (Visit 3 and 4) after the visit procedures have been completed and within the time frame 1-8 hours post morning study medication dose.  
Washouts planned for baseline Visit 2 should be reached also for baseline CMR evaluation conducted in a week prior to visit 2. For CMRs prior to Visits 3 and 4 rescue medication washout needed as for respective clinic visits.
- 12 Reduction of hyperinflation and reversibility testing: Pre- and post-bronchodilator (400 µg salbutamol (albuterol)) spirometry and body plethysmography at Visit 1. [note: hyperinflation at rest defined as  $FRC_{pleth} > 120\%$  predicted, with post-bronchodilator reversibility greater than or equal to 7.5 percentage points at Visit 1 is an inclusion criterion]. Refer to [Appendix 10.3](#).
- 13 Body plethysmography followed by spirometry measurements:  
Visit 2 - Pre-dose measurement: 1 hour prior to inhalation of morning dose of study medication at Visit 2.  
Visits 3 and 4 - Post-dose measurement: 1.5 hour post morning dose of trial medication at Visits 3 and 4.
- 14 Vital Signs: immediately prior to body plethysmography.
- 15 Blood pressure measurement and pulse wave analysis: should be performed during vital signs assessment prior to body plethysmography.
- 16 Medication Use: From medication counter for IMP and rescue medication.
- 17 Telephone contacts: Site staff will telephone the patient prior to patient's scheduled CMR examination and 1-2 days prior to clinic visits to remind them of medication washout and any other requirements.

